| People, Activity, Context & Technology | 
 Users must feel at ease with and perceive the technology as helpful in reaching desired goal.^{168, 169} | 
 Obtaining input from patients, caregivers, and providers in development of tailored culturally sensitive motivational messages needs to be pertinent to the patients and their circumstances |
| Chronic Care Model (CCM) | 
 Identifies the essential elements of a health care system that promote high-quality chronic disease care PINGS-2 intervention will comprise CCM components of delivery system redesign (home BP monitoring, increased follow-up visits, phone text/audio messages), self-management support (patient education, dedicated phone texts), and community resources (guidelines, support groups, local information). | 
 Majority of interventions based on model improved care processes or outcome measures, and reduce health care costs.⁷³ Delivery system redesign (enhanced care coordination) component of model linked to improvements in outcomes.⁷⁴⁻⁷⁷ Self-management support (confidence in one's ability to behave in a way to produce a desirable outcome) component of model has been strongly linked to favorable outcomes.^{74, 78,79} Multiple components of the CCM may influence care. |

E.4. PINGS-2 (Specific Aims 1 and 2)

- Aim 1: To demonstrate the efficacy/effectiveness of the PINGS intervention vs. usual care in achieving improved BP control at 12 months as primary outcome measure among recent stroke survivors receiving care at 10 medical centers (at primary, secondary and tertiary-levels care) in Ghana in a randomized controlled trial.
- Aim 2: To preliminarily assess the effectiveness of the PINGS intervention vs. usual care at improving self-management, medication adherence, quality of life, as well as a reduction in subsequent CVD related re-hospitalizations, & major adverse cardiovascular events as secondary outcomes.

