E.4.10.1. Analysis: Descriptive statistics will be computed for all study variables, including average follow-up time, retention rate, protocol deviations and violations, and will be compared by treatment group. We will use t-test (Wilcoxon rank sum test) for continuous variables and chi-square test for categorical variables to make comparisons between two groups. The primary analysis will be performed according to the principle of intention to treat. However, we will also do per-protocol sensitivity analysis. All outcomes will be modeled using regression analyses adjusted for baseline factors that show imbalance after randomization and compared to analysis that does not adjust for residual baseline differences.^{192,193} A nominal p value of 0.05 or less will be considered as statistically significant in the primary analysis. A linear mixed model with the 12-month outcomes as dependent variable and baseline value as a covariate will be used to test the hypotheses in Aims 1 and 2 adjusting for other baseline covariates that show imbalance. Assessment of the fit of the models will be made using residual and diagnostic plots. We will employ longitudinal data methods (generalized linear mixed models [GLMM]),¹⁹⁴ which account for correlation of outcomes due to repeated measurements & missing at random (MAR) data to study the change in outcomes over time between the two groups. We will model binary (logit link& binomial distribution) and count outcomes (log link and poisson or negative binomial

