distribution) by properly selecting the link and distribution option of the GLMM. In addition, to evaluate sensitivity of study conclusions to missing data, we will use both last value carried forward& multiple imputation methods to estimate single end-point outcome measures and carry out analyses on the complete data set. We will also use the MNAR statement in SAS 9.4 to make sensitivity analysis on the MAR assumption. If we suspect violation of MAR then we will report the most plausible sensitivity analysis results.¹⁹⁵ Trajectory of BP and other related outcomes will be modeled via GLMM. Differences in time to recurrent events between the two groups will be compared using a log-rank test & a Cox proportional hazards (PH) model (we will test for the PH assumption) will be used to adjust for observed confounders& for clustering via frailty models. Additional analyses will assess patients' adherence to intervention and **biological variables, in particular, age of participants, sex (male versus female), cultural, socio-economic and family factors on primary and secondary outcomes such as self-management, medication adherence outcomes.** We will adjust self-reported measures for potential measurement error using standard techniques.¹⁹⁶

E.4.10.2. Management: Data will be captured via REDCap (a free, secure, web-based application) and overseen by a data management and analysis team comprising statisticians at KNUST. Data will be reviewed on a bimonthly basis and issues will be communicated to the project coordinators for prompt resolution.

E.5. Data Safety Monitoring Board (DSMB): We will utilize a DSMB comprised of three experienced external experts (see letters), who will meet twice per year to review the study progress, safety, ethics, and outcomes.

[figure not shown]
E.6. PINGS-2 (Specific Aim 3)

Aim 3: To identify context-specific implementation facilitators and barriers, to understand the implementation context, and craft a theoretically-guided and evidence-based implementation strategies for routine use and policy adoption of the PINGS intervention in Ghana through multiple stakeholder engagements.

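### The sentence assigning the Aim 1 test names a linear mixed model for a yes/no primary endpoint, and the plan does not say which of its binary methods, with which covariates, is primary

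*Combined protocol and SAP*

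**What the plan says.** **Endpoint.** E.4.8 defines the primary outcome as the share of participants below 140/90 mmHg at month 12 and adds longitudinal systolic comparisons alongside it. E.4.9.2 bases the sample size on that share. Table 3 names its primary row after systolic blood pressure, but the row's description gives the 140/90 target.

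**Test for Aim 1.** In E.4.10.1 one sentence links a test to the aims: "A linear mixed model with the 12-month outcomes as dependent variable and baseline value as a covariate will be used to test the hypotheses", continuing "in Aims 1 and 2 adjusting for other baseline covariates that show imbalance".

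**Other methods in E.4.10.1.** After the descriptive statistics, the plan lists a "chi-square test for categorical variables to make comparisons between two groups". A generalized linear mixed model (GLMM) is then introduced "to study the change in outcomes over time between the two groups". The text adds "We will model binary (logit link& binomial distribution) and count outcomes", to be done "by properly selecting the link and distribution option of the GLMM".

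**Covariates.** All outcomes are to be modelled "adjusted for baseline factors that show imbalance after randomization and compared to analysis that does not adjust for residual baseline differences". No covariate list and no definition of imbalance is given.

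**Site.** Randomisation is stratified by site (E.4.9.1). The Aim 1 sentence does not mention site and does not say what its random effects are. Table 3 lists site among the mediators, and clustering is mentioned only for the Cox model.

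**Entry.** E.4.2 and E.4.4 require systolic pressure of at least 140 mmHg at the last clinical encounter and at the screening visit.

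**The concern.** A linear model with a baseline value as covariate is the natural analysis of a pressure in mmHg, not of a yes/no status. Baseline control status cannot be the useful covariate: at screening it is no for everyone, because entry requires systolic pressure of 140 or more. Read with the Table 3 label, the sentence can be taken as a test of mean systolic pressure.

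At stake is which p-value decides the trial. The text allows a chi-square test, a logit GLMM, a linear model on control status, or a linear model on mean pressure. Some of these would carry covariates chosen after randomisation, and adjusted and unadjusted results are to be compared without an explicit statement of which is primary.

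**Working it through.** **1. Reproduce the plan's figure.** Inputs from E.4.9.2: 60% and 44%, two-sided 0.05, 90% power. With p̄ = 0.52 and pooled variance,

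n per arm = [1.960·√(2·0.52·0.48) + 1.2816·√(0.60·0.40 + 0.44·0.56)]² / 0.16²
= (1.3848 + 0.8938)² / 0.0256 = 202.8, so 203 per arm and **406 in total**.

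This matches exactly. The design calculation is for a comparison of two proportions. With 400 evaluable (500 × 0.8), its power is 89.6%.

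**2. What the Aim 1 sentence could mean.**

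| Reading | For | Against |
|---|---|---|
| Linear model on month-12 control status (0/1), baseline pressure in mmHg | Keeps the endpoint of E.4.8 | Baseline value and outcome are then different quantities |
| Linear model on month-12 systolic pressure | Fits linear, baseline value and the Table 3 label | Contradicts E.4.8 and E.4.9.2 |
| Logit GLMM intended for binary outcomes | E.4.10.1 offers it | Introduced for change over time, not assigned to Aim 1 |

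The same sentence covers Aim 2, which includes "reduction in subsequent CVD related re-hospitalizations, & major adverse cardiovascular events as secondary outcomes". Those are events or counts, so linear cannot be meant literally for every outcome. This points to loose drafting.

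**3. Does the choice matter? Simulation on assumed inputs.** From the documents: Table 1 site sizes, 1:1 allocation within site, 44% and 60%, 406 analysed of 500. Everything else is assumed, because the documents give no SD, correlation or covariate list:

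- Baseline systolic pressure normal with mean 150, truncated at 140.
- Systolic SD 15 to 25, baseline correlation 0.2 to 0.5, site SD 3 to 6 mmHg.
- Diastolic mean 82, SD 12, correlation 0.6 with systolic; diastolic effect 0.25 to 0.75 of the systolic effect.
- Ten further baseline covariates, each correlated 0.15 with follow-up systolic pressure.
- Imbalance flagged by a between-arm significance test.

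There were 800 to 2,500 runs per setting. The Monte Carlo standard error is at most √(0.25/800) = 1.8 points, and about √(0.05·0.95/2500) = 0.4 points for null rates from 2,500 runs. Not every row uses every setting.

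| Quantity | 44% vs 60% | 44% vs 52% |
|---|---|---|
| Disagree on significance: logit vs linear on 0/1 status | about 0-3% | about 0-3% |
| Disagree on significance: logit vs mean systolic pressure | about 4-10% | about 24-36% |
| Power: logit with site and baseline pressure | 89-95% | 39-44% |
| Power: mean systolic pressure | 96-99.9% | 49-72% |
| Power gain of fixed site plus baseline pressure over imbalance-chosen covariates, baseline pressure kept in both (points) | -0.6 to 1.7 | 0.5 to 3.0 |
| Power gain of fixed site plus baseline pressure over the unadjusted chi-square (points) | 0.5-5.0 | 2.0-8.2 |

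At 44% vs 56%, logit and mean systolic pressure disagreed in 19-23% of trials.

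Under no effect, rejection rates were 4.3-5.5% (chi-square), 4.0-6.0% (logit) and 4.6-5.7% (mean systolic pressure). Each is 5% within simulation error.

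**The case against.** The strongest defence is that the plan is clear enough in substance. E.4.8 and E.4.9.2 both fix the proportion as primary. E.4.10.1 provides a chi-square test and a logit link for binary outcomes. A linear model on 0/1 status would nearly always give the same answer. The Aim 1 sentence is itself adjusted, with the unadjusted analysis as the comparator. A mixed model with one month-12 outcome per patient needs a grouping factor, and site is the obvious one.

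Most of this stands, and it rules out several stronger readings that a reader might infer:

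- **That the primary endpoint has moved to mean systolic pressure.** The two endpoint statements say otherwise. The Table 3 row carries the 140/90 target, so it is a mislabel and not a second primary.
- **That no binary method is planned.** Two are; neither is named as the Aim 1 test.
- **That site is left out.** It is only not stated, and could be the unspecified random effect.
- **That the imbalance rule costs substantial power.** The Aim 1 sentence always includes the baseline value. If that is pressure in mmHg, fixed covariates gain only about 0-3 points. Gains of up to about 8 points apply only against an analysis without baseline pressure.
- **That type I error or the sample size is wrong.** Neither is shown; 406 reproduces.

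The defence does not supply the missing statement: which test at month 12 decides Aim 1, and with which covariates.

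**Conclusion.** The point holds as a gap in specification. The only test assigned to Aim 1 does not match the binary endpoint, and the binary methods present are not assigned to it. The role of site is unstated. Covariates beyond the baseline value depend on observed imbalance without a list or criterion, and no explicit label says whether the adjusted or the unadjusted result is primary.

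The consequence is small as long as the outcome analysed is control status. It becomes material only if the sentence is followed as a test of mean systolic pressure, and most of all if the true effect is below the planned one. These sizes rest on assumed SDs, correlations and covariates; the mismatch in wording does not.

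**What to change.** Replace the Aim 1 sentence in E.4.10.1 with one primary test, for example:

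> The primary analysis compares BP below 140/90 mmHg at month 12 (yes/no) between arms by intention to treat, using logistic regression with treatment, study site and continuous baseline systolic pressure as prespecified covariates; two-sided 0.05; [one named effect measure] with 95% CI.

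- Name the effect measure now: the odds ratio, or the risk difference standardised from the model. A logit mixed model with the month-12 contrast is an acceptable substitute if it is the one named.
- State which visit's systolic pressure counts as baseline.
- State that the unadjusted chi-square, models with covariates chosen for imbalance, and all other models are supportive only and cannot replace the primary result.
- Reserve the linear mixed model for mean systolic pressure and other continuous outcomes.
- Relabel the Table 3 row as BP below 140/90 mmHg at month 12 (primary), and list systolic pressure as secondary.

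The cost is wording in E.4.10.1 and in Table 3. Site and baseline pressure are already collected. No visits, data or patients are added, and 406 evaluable and 500 enrolled are unchanged.

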C.6. Prelim Data #6: mHealth-based Med Adherence and BP Control in Ghanaian Stroke Patients: In a pilot RCT,^{44,45} we evaluated the feasibility of an mHealth technology-enabled, nurse guided intervention in improving BP control among 60 recent Ghanaian stroke survivors; 30 each in the intervention & standard of care (SC) arms. Participants in the intervention arm received a Blue-toothed UA-767Plus BT BP device & smart phone for monitoring, reporting BP measurements & med intake under nurse guidance for 3 months vs. SC. Tailored motivational text messages were delivered based upon levels of adherence to the medication intake. To control for attention exposure, the SC arm received SMS messages dealing with healthy lifestyle behaviors but not with med adherence. The PINGS intervention was stopped after month 3 & both groups were followed up until month 9. Primary outcome measure was BP control (<140/90mmHg at month 9). Secondary outcome measures included: (i) medication adherence measured using the Medication possession ratio (MPR) at month 9 and (ii) technological glitches. Outcomes: (1) BP control at month 3 by Intention to treat analysis was 20/30 (66.7%) vs 14/30 (46.7%), p=0.12 in the intervention and control arms respectively at interim analysis at end of intervention.⁴⁴ At month 9, proportion on the intervention vs. controls with systolic BP<140mmHg was 22/30(73.3%) versus 13/30(43.3%), p=0.035 in favor of the PINGS intervention.⁴⁵ (2) Medication possession ratio scores at month 3 were better in the intervention arm (0.88 ± 0.40) vs. SC (0.64 ± 0.45) arm (p=0.03), & at month 9 was (0.95 ± 0.16) vs (0.98 ± 0.24), p=0.56. These pilot trial findings support testing an mHealth intervention aimed at improving BP control after stroke in an under-resourced region.^{44,45} We observed a potential signal of efficacy with the intervention, which we have refined further to test within a larger definitive clinical trial in the current proposal.

D. SOLID COLLABORATIVE RESEARCH TEAM

Our interdisciplinary team has been involved in several projects of direct relevance to PINGS-2 research focus. Our interdisciplinary team represents experts in medicine, nursing, public health, health communication, and information technology. (see bios).

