E.4.8. Outcome and Mediator Measures: Primary outcome is proportion of participants with BP<140/90mmHg at 12-months which is the major modifiable step to stroke event rate reduction. We will also conduct longitudinal comparisons of systolic BP in the intervention vs. usual care groups over the course of follow-up evaluations. Participants will be given an appointment encounter solely for collecting evaluation data at the times listed in Figure 1. Trained assessors with no contact to the PINGS study team will perform all study measurements. Potential mediator/moderators of risk factor control and implementation outcomes will also be collected.

E.4.8.1. Physiological/Laboratory Measures

i. BP measurements: Three readings will be taken by trained study coordinators using an automated BP monitor with the patient seated comfortably for 5 min prior to the measurements, following guidelines.^{174,175} Average of the last 2 BP readings will be used as the measure for each visit. Uncontrolled BP is defined as average clinic systolic BP \geq 140 mm Hg or diastolic BP \geq 90 mmHg per guidelines.¹⁷⁶

E.4.8.2. Self-report Measures and Other Information: Self-report measure outcomes will be assessed using validated questionnaires (see Table 3) administered by trained Research Assistants blinded to allocation of study participants to record responses of participants.

Table 3. PINGS-2 Outcomes and Mediators

| Outcomes | Brief Description |
|---|---|
| Systolic Blood Pressure (Primary outcome) | Target goal of <140/90 mmHg measured at baseline, months 3, 6, 9 and 12. Measured by blinded evaluator using an automated BP monitor. |

| | |
|--|---|
| Self-management outcome (Secondary outcome) | Compared between the two groups using the validated Hypertension Self-care Profile questionnaire (HBP SCP) with items that compositely assesses behavior, motivation and self-efficacy of hypertension management. Assessed at months 4, 8 and 12 ($\alpha=.83-.93$, $r=.64$) ¹⁸¹ |
| Medication adherence (Secondary outcome) | Measured using Medication possession ratio ¹⁷⁷ and 14-item Hill-Bone compliance (HBC) to high blood pressure therapy scale with items that assess medication adherence, clinic appointments and salt intake ¹⁷⁸ assessed at months 3, 6, 9 and 12 ($\alpha=.76-.83$, $r=.64$) ^{179,180} MPR and HBC will be measured in both PINGS and usual care arms at stated time points. |

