E.4.8.3. PINGS Intervention Implementation Outcomes: Among the 250 subjects assigned to the PINGS intervention, we will use surveys, qualitative or semi-structured interviews, checklists to assess **six (6)** implementation outcomes proposed by Proctor et al¹⁸⁹ namely (i) **acceptability** (satisfaction with content, complexity, comfort, delivery and credibility of PINGS); (ii) **adoption** (uptake, utilization, intention to try, refusal rates); (iii) **appropriateness** (perceived fit, relevance, compatibility, usefulness); (iv) **feasibility** (suitability for everyday use, practicability); (v) **fidelity** (use checklist to assess whether PINGS was delivered as intended, quality of program delivery); (vi) **implementation cost** (marginal costs of the intervention & delivery strategy). Furthermore, among providers across the 10 study sites, we will assess provider satisfaction level (e.g. assess provider fatigue from breaches in BP thresholds) using Healthcare provider satisfaction questionnaire.¹⁹⁰

E.4.9. Statistical Considerations

E.4.9.1. Randomization: Once eligibility, consent & baseline data are confirmed, participants will be randomly assigned to PINGS intervention vs. usual care in a 1:1 allocation ratio, stratified by study site. An adaptive block randomization scheme will be developed & maintained by the lead study biostatistician. Once a patient is randomized he or she will be entered into the study and included in intent-to-treat analysis. The randomization assignment will be known to the project coordinator, and the statistician in charge of the randomization procedure, but not known to the research assistant who will be conducting participant follow-up assessments.

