E.4.9.2. Power and Sample Justification: Our sample size calculation and power analyses are based on the proportion with BP<140/90mmHg at 12 months, the premier modifiable risk factor for stroke. In a recent pilot study^{44,45} by this group in Ghana, where this proposed study will take place, 60 subjects (30 per group) were randomized to PINGS & control arms with BP<140/90 mmHg at month 9 was 46% versus 40% after withdrawing the PINGS intervention after 3 months.⁴⁵ We anticipate at least 60% BP control rate in the intervention arm (lasting for 12 months) versus 44% control in the usual care arm, using a type I error of 0.05, a power of 90%, & a two-sided test, we need a total of 406 subjects. Assuming 20% loss to follow up, the conservative target for enrollment is 500. We conservatively expect ~50% will not meet eligibility criteria or may decline to participate, so we can potentially recruit over 500 patients from ~ 5,550 stroke patients encountered at 10 hospitals over 4 years.

E.4.10. Data Management and Analysis

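### The last-value-carried-forward sensitivity analysis assumes BP status holds after dropout, which the pilot gives reason to doubt; it can favour PINGS and could become the reported result

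*Combined protocol and SAP*

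**What the plan says.** The endpoint is binary and fixed in time (E.4.8): "Primary outcome is proportion of participants with BP<140/90mmHg at 12-months". BP is measured at baseline and at months 3, 6, 9 and 12 (Table 3), and the patient-level intervention runs for the full 12 months (E.4.5.1).

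In E.4.10.1 the primary analysis is by intention to treat. A linear mixed model for the 12-month outcome tests the Aim 1 and 2 hypotheses, and generalized linear mixed models valid under MAR handle the repeated measures. Missing data are then examined in sensitivity analyses: "we will use both last value carried forward& multiple imputation methods to estimate single end-point outcome measures". An MNAR analysis in SAS is added, but no shift, reference arm or scenario is given. The section closes by saying that, if MAR is suspected to fail, the sensitivity result judged most plausible will be reported. It gives no rule for that judgement.

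Two places report the pilot. C.6: "BP control at month 3 by Intention to treat analysis was 20/30 (66.7%) vs 14/30 (46.7%), p=0.12", at the end of the 3-month intervention. E.4.9.2, for BP below 140/90 at month 9: "46% versus 40% after withdrawing the PINGS intervention after 3 months".

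**The concern.** A PINGS participant who stops and is lost after month 3, 6 or 9 has a last reading taken while using the monitor, reminders and messages. Carrying it forward treats that on-intervention status as the month-12 outcome. The sample size section points the other way: it cites a small month-9 difference after PINGS was withdrawn, then expects a larger one because the intervention will now last 12 months. That reasoning supposes that some benefit fades once PINGS stops.

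A robustness check should be neutral or lean against the intervention. One that can lean towards it may reassure falsely. Because the choice of sensitivity result is left open, this one could also be put forward as the reported finding.

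**Working it through.** **The plan's own figure first.** Inputs from E.4.9.2: "at least 60% BP control rate in the intervention arm (lasting for 12 months) versus 44% control in the usual care arm", and "using a type I error of 0.05, a power of 90%, & a two-sided test, we need a total of 406 subjects". With pooled variance under the null and p̄ = 0.52, n per arm = [1.96·√(2·0.52·0.48) + 1.2816·√(0.60·0.40 + 0.44·0.56)]² / 0.16² = 202.8, so 203 per arm and 406 in total. This matches. The plan continues: "Assuming 20% loss to follow up, the conservative target for enrollment is 500". Exactly, 406/0.80 = 508; enrolling 500 leaves 400 evaluable and 89.6% power, a trivial gap. The planned difference is 16 points and the planned loss 20%.

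**Pilot inputs.**
- Month 3, end of intervention (C.6): 20/30 = 66.7% vs 14/30 = 46.7%, a gap of 20 points.
- Month 9, six months after withdrawal (E.4.9.2): 46% vs 40%, a gap of 6 points.
- Fall: 20.7 points in PINGS and 6.7 in control, a difference in falls of 14 points.

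**Assumptions.** Loss d is equal in the two arms. Completers have the planned rates, 60% and 44%. Those lost are truly at the pilot month-9 rates by month 12, and any on-study reading carried forward is at the pilot month-3 rate. Let f be the fraction of losses before month 3. For these only the baseline value exists, and it is uncontrolled because entry requires systolic BP of at least 140 (E.4.2).

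**Formulas.**
- True rate = (1−d) × completer rate + d × month-9 rate.
- Carried-forward rate = (1−d) × completer rate + d × (1−f) × month-3 rate.
- Net bias in the difference = d × [0.20 × (1−f) − 0.06].

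**All losses after a month-3 reading (f = 0).** At d = 20%, the true rates are 0.8×60 + 0.2×46 = 57.2% and 0.8×44 + 0.2×40 = 43.2%, a difference of 14.0 points. Carried forward, they are 61.3% and 44.5%, a difference of 16.8. PINGS rises by 4.1 points and usual care by 1.3, a net 2.8 towards PINGS. Since the net is d × 0.14, it is 1.4 points at 10% loss and 0.7 at 5%.

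**Effect of timing at d = 20% (true difference 14.0).**

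| Losses before month 3 | PINGS | Usual care | Difference | Net bias |
|---|---|---|---|---|
| 0% | 61.3% | 44.5% | 16.8 | +2.8 |
| 25% | 58.0% | 42.2% | 15.8 | +1.8 |
| 50% | 54.7% | 39.9% | 14.8 | +0.8 |
| 70% | 52.0% | 38.0% | 14.0 | 0 |
| 100% | 48.0% | 35.2% | 12.8 | −1.2 |

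The PINGS rate itself is raised only if f is below 1 − 0.46/0.667 = 31%. The net bias favours PINGS only if f is below 1 − 0.06/0.20 = 70%. Imputing those lost like completers in their own arm, a simple MAR case, gives a difference of 16.0. The carried-forward result exceeds that only if f is below 1 − 16/20 = 20%.

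**Precision of the pilot input.** For the 14-point difference in falls, treating the two time points as independent, the variance is (0.222 + 0.248 + 0.249 + 0.240)/30 = 0.032 and the standard error 17.9 points. The approximate 95% interval is −21 to +49 points. Assuming a within-person correlation of 0.5 narrows it to about −11 to +39. Both include zero.

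**The case against.** A reader might infer that carrying the last value forward is the plan's rule for everyone who leaves, so that dropout inflates the main estimate. The text does not support that. It is one of three sensitivity approaches, beside multiple imputation and an MNAR analysis, and it does not enter the primary analysis.

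A reader might also infer that it always raises the PINGS rate. The table shows that it does not: early losses carry an uncontrolled baseline value.

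Nor does the pilot establish waning:
- With 30 per arm the interval spans zero.
- Month-3 control is read as below 140/90 from the pilot's definition of its primary outcome, which is stated for month 9.
- Systolic-only control at month 9 was 73.3% vs 43.3%, with no visible loss of effect, although this is not the trial's endpoint.
- The gap in medication possession closed by month 9 (0.95 vs 0.98), but through a rise in the control arm rather than a fall under PINGS.

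Missing the month-12 visit is also not the same as stopping. The pilot withdrew PINGS from a whole arm, whereas here someone who misses a visit may keep the monitor, the phone alarms and the weekly messages. Finally, 2.8 points is near the top of the plausible range, because it assigns the whole 20% allowance to people who stopped soon after month 3. The plan does not say whether that allowance includes deaths.

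All of this stands and limits the size and certainty of the point. It does not rescue the method. Its direction depends on dropout timing, which is reason enough not to use it as a robustness check. The other two approaches do not fill the gap: multiple imputation is listed without any departure from MAR, and the MNAR analysis is unspecified.

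**Conclusion.** The point holds as a modest weakness in one sensitivity analysis. If 20% of each arm is lost after a month-3 reading and then follows the pilot's off-intervention rates, the method favours PINGS by about 2.8 points against a planned 16. The figure is 1.4 points at 10% loss and 0.7 at 5%. It shrinks as early losses increase and reverses once more than about 70% of losses in both arms precede month 3. These sizes rest on imprecise pilot rates, equal loss in both arms and completers at 60% and 44%. The point matters mainly because the plan lets a sensitivity result be chosen for reporting without a criterion, and none of the analyses is specified to assume that PINGS participants who stop lose their benefit.

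**What to change.** In E.4.10.1:

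1. Delete last value carried forward.
2. Keep the MAR multiple imputation.
3. Specify the planned MNAR analysis as reference-based multiple imputation. PINGS participants who stopped the intervention and have no month-12 BP are imputed from the usual-care arm given their baseline and observed BPs, and the imputed values are then dichotomised at 140/90.
4. Record the date each PINGS participant stops the intervention, so that stopping is distinguished from a missed visit and the rule can be applied.
5. Replace the open choice of sensitivity result by naming this analysis in advance as the one reported if MAR is doubted.

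The cost is a change of wording and one added date field, with no change to sample size or visits. The downside is that the sensitivity result may be slightly less favourable to PINGS.
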